10.5.4 Pharmacokinetic**PK Parameters**

- The PK Population will include all subjects who undergo PK sampling and have evaluable PK assay results.
- See table 5 for derived Pharmacokinetic parameters

10.6 Appendix 6: Premature Withdrawals & Handling of Missing Data

10.6.1 Premature Withdrawals

Element	Reporting Detail
General	
 A completed subject is one who has completed all phases of the study including the follow-up visit. Withdrawn subjects may be replaced in the study. All subjects who withdraw prematurely from the study/study drug will be documented and the reason for their withdrawal recorded in the final Clinical Pharmacology Study Report (CPSR). All available data collected up until the point of withdrawal, and the follow-up visits will be used in the analyses and will be listed and all available planned data will be included in the summaries according to the populations defined in Section 4 unless otherwise specified.

10.6.2 Handling of Missing Data

Element	Reporting Detail
General	
 Missing data occurs when any requested data is not provided, leading to blank fields on the collection instrument : 
 These data will be indicated by the use of a “blank” in subject listing displays. Unless all data for a specific visit are missing in which case the data is excluded from the table. Answers such as “Not applicable” and “Not evaluable” are not considered to be missing data and should be displayed as such.
Outliers	
 Any subjects excluded from the summaries and/or statistical analyses will be documented along with the reason for exclusion in the clinical study report.

10.6.2.1 Handling of Missing Dates

Element	Reporting Detail
General	Partial dates will be displayed as captured in subject listing displays.
Adverse Events	
 The eCRF allows for the possibility of partial dates (i.e., only month and year) to be recorded for AE start and end dates; that is, the day of the month may be missing. In such a case, the following conventions will be applied for calculating the time to onset and the duration of the event: 
 Missing Start Day: First of the month will be used unless this is before the start date of investigational product; in this case the study treatment start date will be used (and hence the event is considered

Element	Reporting Detail
	
On-treatment as per Appendix 3: Treatment States and Phases).
 
 • Missing Stop Day: Last day of the month will be used, unless this is after the stop date of study treatment; in this case the study treatment stop date will be used. • Completely missing start or end dates will remain missing, with no imputation applied. Consequently, time to onset and duration of such events will be missing. • AEs with entirely missing or unknown start dates will be assumed to be on-treatment for reporting. • AEs with missing end dates are not anticipated to affect reporting.

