8.1.1. Time period and Frequency for collecting AE and SAE information

- AEs and SAEs will be collected from the start of informed consent until the follow-up contact, at the time points specified in the Time and Events Table (Section 7.1).
- AEs and SAEs collected before the start of study treatment will be recorded as pre-treatment AEs/SAEs.
- Any SAEs assessed as related to study participation (e.g., protocol-mandated procedures, invasive tests, or change in existing therapy) or related to a GSK product will be recorded from the time a subject consents to participate in the study up to and including any follow-up contact.
 - All SAEs will be recorded and reported to the sponsor or designee immediately and under no circumstances should this exceed 24 hours, as indicated in [Appendix 2](#). The investigator will submit any updated SAE data to the sponsor within 24 hours of it being available.
- Investigators are not obligated to actively seek AEs or SAEs in former study subjects. However, if the investigator learns of any SAE, including a death, at any time after a subject has been discharged from the study, and he/she considers the event reasonably related to the study treatment or study participation, the investigator must promptly notify GSK.

NOTE: The method of recording, evaluating and assessing causality of AEs and SAEs plus procedures for completing and transmitting SAE reports to GSK are provided in [Appendix 2](#).

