10.6.2.2 Handling of Partial Dates

Element	Reporting Detail
Concomitant Medications	
 • Partial dates for any concomitant medications recorded in the CRF will be imputed using the following convention: 
 • If the partial date is a start date, a '01' will be used for the day and 'Jan' will be used for the month • If the partial date is a stop date, a '28/29/30/31' will be used for the day (dependent on the month and year) and 'Dec' will be used for the month. • The recorded partial date will be displayed in listings.
Adverse Events	
 • Any partial dates for adverse events will be raised to data management. If the full date cannot be ascertained, the following assumptions will be made for calculating the time to onset and the duration of the event: 
 • If the partial date is a start date, a '01' will be used for the day and 'Jan' will be used for the month, unless this is before the start date of investigational product; in this case the study treatment start date will be used (and hence the event is considered on-treatment as per Appendix 3: Treatment States). • If the partial date is a stop date, a '28/29/30/31' will be used for the day (dependent on the month and year) and 'Dec' will be used for the month, unless this is after the stop date of study treatment; in this case the study treatment stop date will be used. • The recorded partial date will be displayed in listings.

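### The SAP's partial-date rules class an adverse event as on-treatment even when its recorded month is known to precede first dose

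*SAP*

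**What the plan says.** SAP 10.6.2.1 describes the missing information: "The eCRF allows for the possibility of partial dates (i.e., only month and year) to be recorded for AE start and end dates". So the day is unknown, but the month and year are known. For a missing start day the rule is: "First of the month will be used unless this is before the start date of investigational product". When the imputed date does precede the start, "in this case the study treatment start date will be used (and hence the event is considered" on-treatment.

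SAP 10.6.2.2 covers AE partial dates again. It begins with a query step: "Any partial dates for adverse events will be raised to data management". If the full date cannot be found, it fills a start date with day 01 and, for the month, "Jan' will be used for the month, unless this is before the start date of investigational product", with the same fallback to the treatment start date. It adds: "The recorded partial date will be displayed in listings".

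Two other places define what a pre-treatment event is. SAP Appendix 3 classes anything dated before the start of study treatment as pre-treatment. Protocol 8.1.1 collects AEs from consent and states: "AEs and SAEs collected before the start of study treatment will be recorded as pre-treatment AEs/SAEs".

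**The concern.** The fallback to the treatment start date makes sense when the recorded month is the month of first dose, because the true onset could then lie on either side of dosing. It does not make sense when the recorded month had already ended, or when a known stop date precedes dosing. In those cases the onset is known to be before treatment, and the rule overrides that knowledge.

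Adverse events are a primary endpoint. What is at stake is the treatment state, time to onset and duration of a baseline event, which could be presented as starting on the day of first dose. Two further points concern the same text. The two sections can be read as giving different answers for the same AE. And the SAP summarises AEs by dose group without saying how an AE with an incomplete date is linked to one of the up to four Part A periods.

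**Working it through.** The plan gives no figure to reproduce, so the rules were applied as written.

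**Inputs**
- Screening is Days -28 to -2 (protocol 7.1, Tables 1 and 2). AEs are collected from consent (protocol 8.1.1).
- AE duration = resolution date - onset date + 1 (SAP Appendix 3).
- Part A: up to four periods per cohort, initially 14 days apart (protocol 4.1).
- Assumed for illustration: first dose on 20 April 2017, and all onset days equally likely.

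**1. The rule as a formula.** Imputed onset = the later of (first of the recorded month, treatment start). This can never be earlier than treatment start, so no AE with a missing start day can be classed as pre-treatment, whatever month was recorded.

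**2. Example.** With first dose on 20 April, Day -28 is 23 March. An AE recorded as March 2017 is imputed to 1 March. That precedes 20 April, so onset becomes 20 April and the AE is on-treatment. If its stop date is known to be 25 March, duration = 25 March - 20 April + 1 = -26 + 1 = **-25 days**.

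**3. How often the recorded month precedes the first-dose month.** Take all 365 first-dose days in a year and each onset b = 1 to 28 days before dosing: 365 × 28 = 10,220 combinations. The onset falls in an earlier month when the first dose is on day b of its month or sooner, which gives 12b combinations for each b. The sum is 12 × (28 × 29 / 2) = 12 × 406 = 4,872, and 4,872 / 10,220 = **48%**. The rule moves all 4,872 to the first-dose date.

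**4. The two sections side by side.** First dose on 20 April; AE recorded as May 2017.

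| Rule | Imputed onset |
|---|---|
| 10.6.2.1 | 1 May |
| 10.6.2.2, *Jan* always replacing the month | 1 January, then moved to 20 April |
| 10.6.2.2, *Jan* only if the month is missing | 1 May |

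The text does not say which reading of 10.6.2.2 applies.

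**5. Part A, conditional.** Suppose that an AE is assigned to the last dose on or before its imputed onset, and that treatment start means the subject's first dose. The SAP states neither. With doses on 20 April, 4 May, 18 May and 1 June, an AE on 20 May (after dose 3) recorded as May goes to 1 May under 10.6.2.1, hence to dose 1. An AE on 5 June recorded as June goes to 1 June and stays with dose 4. In general, an AE q days after a later dose (q = 0 to 13) stays with that dose only if a first-of-month falls within the q + 1 days from dose to onset. The mean of q + 1 is 7.5, so the chance is 7.5 × 12 / 365 = 25%, and **75%** of later-period AEs with a missing day would move to an earlier dose.

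**The case against.** The strongest reply is that few events will be touched and that the default is cautious. Partial dates are queried before any imputation, and listings keep what was recorded. Part A subjects stay in the unit for 72 hours after each dose, and Part B subjects are in-patients or seen daily during dosing. The SAP also treats AEs with entirely missing start dates as on-treatment, a common safety convention. The stated purpose of the imputation is time to onset and duration, and none of the listed AE tables is restricted to on-treatment events, so the documents do not show that a table cell would change.

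Most of this stands as a limit on size. It does not rescue the rule. A cautious default is for uncertain timing, and here the timing relative to dosing is known. Close supervision around dosing helps less in the screening interval, which is where the error arises. Queries and listings do not correct the derived state, onset or duration of an event that stays unresolved.

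A reader might infer more than the documents support:
- *Every partial-date AE in the year of first dosing lands on the first dose.* This needs the literal reading of the January rule. The matching stop-date text makes the last day depend on the month and year, which would be pointless if December always replaced the month. That favours filling only the missing component, so the text is ambiguous rather than plainly wrong.
- *Later Part A events do move to earlier doses.* This follows only under the two assumptions in step 5 of the working.
- *The shift is toward the lowest dose or placebo.* Cohort 2 starts after Cohort 1, so its first period need not be the lowest dose, and a subject given active first and placebo later would shift toward active.
- *One moved event is worth 12.5 points between doses.* That is 1 of 8 active subjects in a Part B cohort, where each subject has a single period and no shift between doses is possible.

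**Conclusion.** The core point holds on the wording alone. Both sections assign the treatment start date, and hence on-treatment status, to AEs whose recorded month or known stop date shows that they began before first dose. This conflicts with SAP Appendix 3 and protocol 8.1.1 and can produce negative durations.

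The 48% is the share of pre-dose onset days exposed to the error if the day is missing and onset days are equally likely. It is not an estimate of how many AEs will be affected. The documents give no rate of unresolved partial dates, and the number is probably small.

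Two lesser points need clarification rather than correction: whether the January rule can override a known month, and how Part A AEs with partial dates are assigned to a dose. The 75% shows only why the second needs an explicit rule. The matter should be corrected before the analysis datasets are built, but nothing here suggests that it would change the main safety conclusions.

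**What to change.** Merge SAP 10.6.2.1 and 10.6.2.2 into one AE rule:
1. Use *Jan* or *Dec* only when the month itself is unknown; keep a recorded month.
2. Keep an AE pre-treatment when its known month and year, or its stop date, is before first dose.
3. Substitute the treatment start date only when the recorded month is the month of first dose and the stop date does not precede that dose.
4. In Part A, assign an AE with a partial date to the dosing period or visit at which it was recorded, not by the imputed date. State how an AE first reported at admission, before that period's dose, is handled.

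In the enumeration, items 2 and 3 reduce earlier-month AEs classed as on-treatment from 4,872 of 4,872 to none. The other 10,220 - 4,872 = 5,348 combinations (52%) remain on-treatment by default. Their month contains the first dose, so without a stop date their timing really is unknown and the cautious default is reasonable. These items leave the conditional 75% for Part A unchanged, which is why item 4 is needed.

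The cost is SAP wording and the matching date derivation. No new data are needed, assuming that AE records can be linked to the visit or period at which they were entered.

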Study Design	
A double blind (sponsor unblind), randomised, placebo-controlled first time in human, dose escalation study enrolling healthy adult subjects.
 
Part A: Subjects will receive single doses of GSK3036656 or matching placebo.
 
It will include up to two cohorts. Each cohort will participate in up to 4 treatment periods (including a food effect treatment period).
 
Up to 18 subjects (9 in each cohort, 6A:3P) (excluding possible replacements) will be recruited into the single ascending dose part of the study.
 
Part B: Subjects will receive repeat doses of GSK3036656 or matching placebo.
 
It will include up to four cohorts. Each cohort will participate in only one treatment period.
 
Up to 40 subjects (10 in each cohort, 8A:2P) (excluding possible replacements) will be recruited for the repeat dose.
 
The total duration of the study will be approximately 12 weeks for subjects recruited into Part A and approximately 8 weeks for subjects recruited into part B.

Planned Analyses	
 Interim Analysis 
No formal interim analysis is planned for this study, however, safety, tolerability, and pharmacokinetic data will be reviewed before each dose escalation in Part A (single dose) and Part B (repeat dose), and prior to the investigation of the food effect.
 
 The final planned analyses will be performed, as defined in this RAP document, after database freeze has been declared.
Analysis Population	
 Enrolled Population: Defined as all subjects who were enrolled for the trial irrespective of whether they were randomized or not and for whom a record exists on the study database. Safety Population: Defined as all randomised subjects who receive at least one dose of study medication. If subjects receive a treatment different to their randomised treatment, they will be analysed according to the treatment actually received.

Overview	Key Elements of the Reporting and Analysis Plan
	
 • Pharmacokinetic (PK) Population: Subjects in the Safety population who administered at least one dose of active treatment and have at least one evaluable PK sample.
Hypothesis	No formal hypotheses will be tested.

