10.3 Appendix 3: Treatment States

10.3.1 Treatment States

Assessments and events will be classified according to time of occurrence relative to the start and/or stop date and time of the study treatment.

Treatment State	Definition
Pre-Treatment	Date and time < Study Treatment Start Date and time
On-Treatment	If onset date is on or after treatment start date and time & on or before the treatment stop date and time Study Treatment Start Date and time \leq Date and time \leq Study Treatment Stop Date and time
Post-Treatment	If onset date and time is after the treatment stop date and time Date and time > Study Treatment Stop Date and time
AE Onset Time Since First Dose (Days)	If Treatment Start Date > AE Onset Date = AE Onset Date - Treatment Start Date If Treatment Start Date \leq AE Onset Date = AE Onset Date - Treatment Start Date +1 Missing otherwise
AE Duration (Days)	AE Resolution Date – AE Onset Date + 1
AE Drug-related	If relationship is marked ‘YES’ on eCRF or value is missing.

NOTES:

- If the study treatment stop date is missing then the AE will be considered to be On-Treatment.

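### Unresolved partial AE stop dates are capped at treatment stop with no floor at onset, so an AE starting after treatment stop gets a zero or negative duration

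*SAP*

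**What the plan says.** SAP 10.6.2.1 covers AE dates with a missing day and states the purpose: "the following conventions will be applied for calculating the time to onset and the duration of the event". For a missing stop day the base rule is "Last day of the month will be used", qualified by "unless this is after the stop date of study treatment; in this case the study treatment stop date will be used". SAP 10.6.2.2 has the same cap for partial AE stop dates and extends the base rule to a missing month (December). It applies only after data management has been asked for the full date and cannot obtain it.

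SAP 10.3.1 computes AE duration as "AE Resolution Date – AE Onset Date + 1". The same table defines a Post-Treatment state, "If onset date and time is after the treatment stop date and time", so the plan expects AEs to begin after dosing has ended. Protocol 8.1.1 collects AEs up to the follow-up contact, which Protocol 4.1 and 4.2 place about 14 days after the last dose.

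On dosing, the SAP synopsis says "Part A: Subjects will receive single doses of GSK3036656 or matching placebo" and "Each cohort will participate in up to 4 treatment periods (including a food effect treatment period". Part B gives daily doses for up to 14 days.

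**The concern.** An AE does not end because dosing ends. The cap treats treatment stop as the latest possible resolution date, while the same plan collects and classifies AEs that begin later. For those AEs the imputed resolution precedes the onset, and the duration formula, whose smallest valid value is 1 day, returns 0 or less.

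The setting makes this more than a corner case of the rule. After a single dose, the time on treatment within a period is one day and nearly all of the observation time is post-treatment. AEs are also a primary endpoint of a first-in-human study. What is at stake is whether a derived safety variable is valid, not any planned comparison.

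**Working it through.** The plan gives no figure to reproduce, so the check applies its rule to dates. All calendar dates below are illustrative assumptions.

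**Rule.** Imputed stop = the earlier of (a) the last day of the recorded month and (b) the treatment stop date. Duration = imputed stop - onset + 1.

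**General result.** Let onset be k days after treatment stop, with k at least 1. The true end is on or after onset, and the end of the recorded month is on or after the true end. Month-end is therefore later than treatment stop and the cap always applies. Duration = 0 - k + 1 = 1 - k, whatever the calendar date or true duration. Onset on the stop date itself (k = 0) gives 1 day.

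**Single dose, stop date taken as the dosing date.** Dose on 10 March, each AE truly lasting 5 days, stop recorded as March:

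| Onset | k | Duration under the rule | Month-end with no cap |
|---|---|---|---|
| 10 March | 0 | 1 | 22 |
| 11 March | 1 | 0 | 21 |
| 12 March | 2 | -1 | 20 |
| 13 March | 3 | -2 | 19 |
| 24 March | 14 | -13 | 8 |

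Across the 15 onset days k = 0 to 14, one gives 1 day, one gives 0, and 13 (13/15 = 87%) give a negative value. This is a count of possible onset days, not a forecast of how often it will happen.

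**Part B.** Day 1 = 1 March, last dose Day 14, AEs truly lasting 5 days. Duration = 14 - onset day + 1 = 15 - onset day:

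| Onset day | Duration under the rule |
|---|---|
| 5 | 10 |
| 12 | 3 |
| 14 | 1 |
| 15 | 0 |
| 16 | -1 |
| 28 | -13 |

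The Day 12 and Day 14 rows show truncation of AEs that begin on treatment and outlast it. The Day 5 row shows the opposite error: month-end imputation overshoots, and the cap only partly corrects it.

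**Conflict with the recorded month.** Dose 28 March, onset 29 March, stop recorded as April. Month-end is 30 April, capped to 28 March, so the imputed date falls outside the month on the form. Duration is 28 - 29 + 1 = 0. Had the AE ended on 3 April, it would truly have lasted 6 days.

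**Which stop date in Part A.** Take four doses 14 days apart: 1, 15 and 29 March, and 12 April. Consider an AE starting 3 days after a dose.
- Stop date per period: duration is 1 - 3 = -2 in every period.
- Stop date overall (12 April): in period 1, onset is 4 March and month-end 31 March is before 12 April, so duration is 31 - 4 + 1 = 28. In period 4, onset is 15 April and the stop is capped to 12 April, so duration is 12 - 15 + 1 = -2.

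On the overall reading, similar AEs get 28 or -2 days depending only on the period.

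**The case against.** The strongest reply is that nothing reported depends on this. SAP Table 6 and Tables 3.1 to 3.12 count subjects and occurrences. Treatment state is set by onset, so no AE is reclassified. Listings show the date as recorded. Partial dates are queried first, and missing stop days should be rare, because Part A subjects stay in the unit to 72 hours and Part B subjects are resident or attend daily during dosing. All of this stands, and it is why the point is minor. It does not make the rule correct: the SAP defines duration and sets out an imputation for it. Whether the AE listing prints duration depends on a sponsor shell that is not in the documents. The remark in 10.6.2.1 that missing end dates should not affect reporting does not repair the derived value.

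Three stronger readings are tempting and are not supported:
- **The rule always makes AEs look briefer.** It always shortens relative to month-end imputation when it bites, but not relative to the truth: the 5-day AE from Day 5 in Part B becomes 10 days. No consistent bias in favour of the drug follows.
- **Every Part A AE starting after the dosing day gets an impossible duration.** This assumes a complete loss of the stop day and a stop date set per period. The SAP never says which stop date is meant, and on the overall reading impossible values arise only after the final dose.
- **Any Part B AE continuing past Day 14 is cut to Day 14.** Complete stop dates are untouched.

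A further fair objection concerns the remedy. Month-end alone turns the 5-day AEs above into 19 to 22 days for onsets within 3 days of the dose. A cap at the follow-up visit alone would truncate the serious AEs and AEs of special interest that Protocol 8.1.3 follows to resolution or stabilisation. The fix has to allow for both.

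**Conclusion.** The rule is wrong as written. For an AE that starts after treatment stop and has an unresolved partial stop date, the imputed resolution precedes onset: duration is 0 for next-day onset and negative from two days on. An AE that begins on treatment and outlasts it is cut at the stop date, and the imputed date can contradict the recorded month.

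The 1 - k result needs only an onset k days after treatment stop and does not depend on the example dates. The Part B rows assume that dosing runs to Day 14; after an earlier stop the same pattern starts earlier. The reach in Part A depends on the undefined stop date. The number of affected AEs cannot be derived from the documents but should be small, and the consequence is confined to derived AE duration.

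**What to change.** In SAP 10.6.2.1 and 10.6.2.2, drop the treatment-stop cap and use this rule:
- Impute the last day of the recorded month, or of the recorded year if the month is missing.
- Cap it at the subject's last contact date, meaning the follow-up visit or any later AE follow-up contact, whichever is later.
- Never set it earlier than the AE onset date or the start of the recorded month or year.

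In SAP 10.3.1, state whether the Part A study treatment stop date is per period or overall.

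Check on the single-dose example, assuming 10 March is the subject's final dose and the last contact is 14 days later, on 24 March: duration becomes 24 - (10 + k) + 1 = 15 - k. That is 13 days for the 12 March onset and 1 day for a 24 March onset. Every value is at least 1. Durations can still be overstated (13 against a true 5), so imputed durations should be read as upper limits.

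The cost is one sentence in each of two SAP tables, one clarifying line in 10.3.1 and a small programming change. No data collection or clinical procedure changes.
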